**Clinical** providers may refer interested patients and document their willingness to be contacted by the study through CPRS via their progress notes and using templated language provided to them (See Appendix G). Clinicians may also send referral information via encrypted email with the same templated documentation (or comparable documentation that the Veteran is interested in hearing more about the study and gives permission for research staff to contact them). Following a chart review and preliminary phone screen to determine eligibility, potential participants will be scheduled for an initial telehealth (by video or telephone) appointment during which they will be consented to the study. Consented participants will be instructed to return the informed consent form (ICF) and Authorization for Use and Release of Individually Identifiable Health Information Collected for VHA Research (HIPAA form) to the study team using a prepaid and preaddressed envelope. Once received, a study team member will complete an assessment appointment with the participant via telehealth. After all eligibility criteria are met and the assessment is complete, if telehealth appointments are conducted via VA Video Connect (VVC) platform, participants may receive automated reminders and appointment links over email, consistent with procedures for clinical appointments using VVC. The study statistician will randomly assign eligible participants to one of the two treatment options and will notify the site study coordinator about randomization status. The site study coordinator or other appropriate research team member, will contact the participants to inform them of their group assignment. Those assigned to CABA will be contacted by their therapist and tele-or video-therapy will commence. Those assigned to TAU will be offered a referral for PTSD specialty care. The assessors will be blind to group status throughout the study whenever possible. Consistent with a national VA performance measure that requires 8 sessions to be delivered over a 14 week period, participants will be contacted by phone by a blinded assessor for the mid-treatment assessment 7 weeks after the onset of treatment. Allowing 14 weeks to complete a 10 session treatment protocol accounts for cancellations and missed sessions. Participants will then be seen for follow-up assessments 14 weeks after initiating treatment. In order to minimize drop-out and maximize retention of individuals for intent-to-treat analyses, extensive efforts will be made to stay in contact with all study participants, including individuals who drop out of treatment. CABA participants who are deemed nonresponders or relapsers (do not evidence at least a 20% reduction in PTSD or cognitive symptoms) at the post-assessment or follow-up assessment (or an increase in suicidality or substance abuse), and other participants as clinically appropriate, will be offered alternative treatment or appropriate referrals.

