## **Adequacy of Protection from Risks**

### **a. Protection Against Risk**

Trained, closely supervised staff will conduct the assessments and the intervention. Assessors conducting diagnostic psychiatric interviews will have at least one year of graduate experience or equivalent work experience, and therapists will be master's or doctoral level. Drs. [name] and [name], licensed clinical psychologists, will review weekly therapy tapes and attend to any difficulties encountered. In addition, participants will be provided with emergency contact numbers. Finally, all participants will be clearly informed of their right to withdraw at any point and Drs. [name] and [name] will recommend termination of participation (and provide appropriate referral and follow-up) if substantial decline in functioning is observed (including significant increase in alcohol or drug use). Referral will also be offered to nonresponders and any participant who requests further treatment. Specific procedures will be maintained to maximize the likelihood that participant research related material will be secure and confidential. Data will be stored in locked filing cabinets and computer databases, without names or other potentially identifiable information attached; identifiable information will be kept separately and a coding system will be used to link data and identifiers.

All SAE's, UAP's, and protocol deviations occurring at either site will be communicated to the Co-PI's immediately and necessary documentation will be submitted to the CIRB within stipulated timeframes and via designated channels in accordance with the VA Central IRB Table of Reporting Requirements.

All study personnel will follow the policies and procedures for suicide prevention and management of suicidal behavior and its aftermath anywhere within the medical center or on the premises as outlined in the VAPORHCS Medical Center Memorandum No. 11-04 and in Memorandum TX-74 for Seattle both included in the study Suicide behavior protocol, Appendix A.

**Imminent risk Protection:** The following protocol applies to participants who express indication of imminent risk or clinical emergency; this includes concerns about suicidality and homicidality.

Participants may express indicators of risk either to the study clinician or to the study assessor; the protocol differs for each of these groups and is discussed below:

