See Table 3 in section B “Data Collection and Assessment” below for a schedule of administration for each measure. Participants will be sent a response key via postal mail (see documents **Survey Response Key** and **Response Key Cover Letter**). Staff will read the questions to participants, who will respond to each item with the aid of the response key. If the response key is lost, a new one may be sent to them.

**Telephone Reminder Calls (Visits 1-14):** The site coordinator or designated study staff member will contact participants by phone to remind them of the initial visit, mid-treatment assessment, and post-treatment assessment. CABA therapists may contact participants 1-2 days prior to treatment session to remind them of upcoming appointment; participants who are using VA Video Connect for the CABA sessions may also receive automated reminders of the appointment via email. Participants assigned to TAU will get standard VA reminder calls.

**Visits 2-6 and 8-12:** During visits 2-6 and 8-12, subjects will attend weekly 90-minute individual sessions of the CABA intervention via telehealth and TAU (at a minimum, the opportunity to attend 10 90-minute individual sessions).

**Documentation in CPRS:** A Research Screening/Enrollment/Disenrollment note will be entered into CPRS for all Veterans who consented into the study. An additional note documenting informed consent, completion of intake procedures, eligibility determination, and next steps will also be entered into CPRS following the baseline/intake visit. Disenrollment notes will be entered into CPRS at the completion of each Veteran’s participation in the study. Veteran assigned to the CABA condition will have session appointments entered into a research clinic and the study therapist will enter a note into CPRS summarizing the session content for each CABA treatment session.

**Compliance:** Attendance will be recorded. Financial compensation and reminder calls will be used.

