**Hypothesis 1a)** PTSD symptom severity. Dependent variables: CAPS-V and PCL-5.

**Hypothesis 1b)** Functional impairment. Dependent variables: HVLTR, WAIS-IV (Digit Span subtest), DKEFS (Trails subtest), and COWAT (Verbal Fluency).

Independent variables: Treatment group (2 levels, CABA and TAU), & Time (3 levels, Weeks 0, 7, and 14). Statistical Analysis: We will analyze data on all randomized subjects in whom we have a baseline assessment and at least one post-baseline evaluation by Mixed effects model methods. Preliminary inspection of data will determine whether the outcome is nearly normal, or whether an appropriate transformation is required, or whether a generalized linear mixed model should be considered. The mixed effects model method provides an estimate of the individual variability around the population trend, the variability of the individual intercepts (baseline values) and slopes (changes across time), and the correlation between them. A fully saturated treatment by time model will be utilized for inference. Covariance structure will be chosen based on Akaike's Information Criterion (AIC). Random group level treatment effects will also be evaluated for importance based on the model AIC. This allows for any group level effects to be incorporated into the model. Denominator degrees of freedom will be calculated using the Kenward-Roger small sample correction. The design is a 2 (sites) X 2 (CABA vs TAU) X 3 (baseline, 7, and 14 weeks). The interaction of Site and Treatment X Site will be included and tested as

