### 5.7 Withdrawal of Subjects

Should any findings arise during assessment study visits which might affect the participant’s health or welfare, the study team will address those findings directly with participants during the assessment study visit within which the issues are discovered. The study team will use CPRS to identify the participant’s health care providers as well as communicate the findings with those providers and follow-up via telephone as needed.

The co-PIs will recommend termination of participation, provide appropriate referrals, and engage in follow-up if substantial decline in functioning is observed at any assessment study visit for all participants and/or treatment visits for those assigned to the CABA treatment intervention. Participation in this study therefore, will be terminated at the discretion of study personnel (with final determination by co-PI’s), based upon clinical observations and judgments regarding the safety of continued participation to the patient’s physical and/or psychological health and well-being. Additionally, if participants fail to comply with important instructions that are part of the approved study protocol, such as actively abusing substances, participation will be terminated without consent.

Although the proposed study poses no serious risks to participants, participants may notify research personnel about pre-existing mental health issues that have not been previously identified by other VA providers. Therefore, participants will be referred to the VA’s Mental Health Division for further

assessment and/or treatment if a previously undiagnosed psychiatric disorder is identified. We will inform participants of this procedure as part of the informed consent process and participants must agree to this procedure to be eligible to participate in the study. This ensures that we can adequately manage any pre-existing clinical issues that become apparent through subject evaluation.

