If a participant chooses to withdraw from the study, study personnel or Drs. [name] or [name] will refer the patient back to their providers in Primary Care for further assessment of treatment needs. The reason for withdraw will be documented. Participants who choose to withdraw early will still be allowed to continue participation in follow-up assessments and would continue to receive financial reimbursement for doing so, but this would be completely voluntary. A possible consequence of a participant choosing to withdraw early from the study is that he/she will likely continue to experience cognitive and/or PTSD symptoms. Without treatment, these symptoms may worsen over time.

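### Non-compliance ends study participation rather than study treatment, with no provision for later assessment, so week-14 CAPS-V and cognitive data can be lost needlessly

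*Combined protocol and SAP*

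**What the plan says.** Section 5.7 (Withdrawal of Subjects) gives two grounds on which the investigators may end participation.

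- **Decline in functioning.** The co-PIs recommend termination, refer the participant and follow up. Decline is looked for "at any assessment study visit for all participants and/or treatment visits for those assigned to the CABA treatment intervention".
- **Non-compliance with important instructions.** Here the wording is mandatory: "such as actively abusing substances, participation will be terminated without consent".

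The section then turns to voluntary withdrawal: "Participants who choose to withdraw early will still be allowed to continue participation in follow-up assessments", with payment. It says nothing about assessments for participants whom the investigators remove.

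Three other places bear on the point.

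- Section 5.1, Procedures, promises for the sake of intent-to-treat analysis that "extensive efforts will be made to stay in contact with all study participants, including individuals who drop out of treatment".
- Table 3 schedules CAPS-V and the NP battery at weeks 0 and 14 only. PCL-5, NSI, BDI-II and SLS are also taken at week 7.
- Section 5.6, under hypotheses 1a and 1b, states: "We will analyze data on all randomized subjects in whom we have a baseline assessment and at least one post-baseline evaluation".

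**The concern.** In a randomised comparison, stopping a treatment need not mean stopping measurement. The non-compliance clause joins the two. Staff who apply it literally would have no stated basis for inviting a removed participant to the week-7 or week-14 assessment.

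The stated trigger, active substance abuse, is plausibly linked to poor PTSD and cognitive outcomes. Section 5.6 itself accepts that the mixed model is robust only while the cause of missingness is not informative. The planned pattern-mixture check does not solve this for CAPS-V or hypothesis 1b. A pattern with only a baseline value contains no information on change, so an estimate for it has to be assumed.

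The clause is also stricter than the rest of the protocol. Medication changes after enrolment do not end participation (Section 5.4), starting another therapy does not lead to being dropped (Section 5.3), and Section 5.1 describes substance use as something CABA can target.

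**Working it through.** **1. How the protocol treats substance use after enrolment**

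| Place | Event | Consequence |
|---|---|---|
| Protection Against Risk | Termination recommended "if substantial decline in functioning is observed (including significant increase in alcohol or drug use") | Referral and follow-up |
| Section 5.1, Procedures | At post- or follow-up assessment: "or an increase in suicidality or substance abuse), and other participants as clinically appropriate, will be offered alternative treatment or appropriate referrals" | Offer of treatment or referral |
| Section 5.7 | Active substance abuse as non-compliance | Participation ended, mandatory |

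Only the third makes the end of participation automatic. None of the three says whether a removed participant is still assessed.

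**2. Data left if a participant is removed before week 14 and not assessed (from Table 3)**

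| Outcome | Planned after baseline | Removed before week 7 | Removed after week 7 |
|---|---|---|---|
| CAPS-V (1a) | 1 | 0 | 0 |
| NP battery (1b) | 1 | 0 | 0 |
| PCL-5 (1a) | 2 | 0 | 1 |

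**3. Size of a possible bias**

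The plan gives no removal rate, so there is no figure to reproduce. Inputs from Section 5.6 are 96 per arm, a design effect of 0.5 SD at the last time point, and an autoregressive correlation of 0.45 between sequential assessments. The rest is assumed:

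- D, the number removed and unassessed in CABA minus that in TAU, runs from -4 to +4.
- g, the amount by which removed participants are worse at week 14 than the rest of their arm, runs from 0.5 to 1.0 SD and is the same in both arms.
- Removed participants do not differ at baseline. If they were already worse then, the shift in change would be smaller.

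For CAPS-V, shift = (D / 96) x g. A positive value favours CABA and a negative one favours TAU.

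- D = 0: shift 0. Data are lost, but the comparison is not biased.
- D = ±1, g = 0.5: 1/96 x 0.5 = ±0.005 SD, and 0.0052 / 0.5 = 1.0% of the design effect.
- D = ±4, g = 0.5: 4/96 x 0.5 = ±0.021 SD (4.2%).
- D = ±4, g = 0.75: 4/96 x 0.75 = ±0.031 SD (6.3%).
- D = ±4, g = 1.0: 4/96 x 1.0 = ±0.042 SD (8.3%).

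For PCL-5, removal before week 7 gives the same figures. After week 7 the retained value carries part of the information. If the gap at week 7 is already g, the shift is (D / 96) x g x (1 - 0.45), so the largest value is 0.0417 x 0.55 = ±0.023 SD. If the week-7 gap is half of g, it is 0.0417 x (1 - 0.225) = ±0.032 SD.

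**4. Loss of precision**

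With 15% drop-out, 0.85 x 96 = 81.6 per arm remain. Take a week-14 comparison adjusted for baseline, two-sided alpha 0.04, effect 0.5 SD, and baseline correlation 0.45² = 0.2025 (an assumption). Power = Φ(0.5 / √[2(1 - 0.2025²)/n] - 2.054), which is 88.6% at n = 81.6. Five further percentage points of loss leave 76.8 per arm and 86.7%. Precision is therefore not the main issue.

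**The case against.** The strongest reply is that silence is not prohibition. Section 5.7 does not forbid assessing a removed participant, and the paragraph on voluntary withdrawal contains no word limiting assessments to that group. A reader might infer that paid assessments are reserved for those who withdraw by choice, but the text does not go that far. The retention statement in Section 5.1 speaks of all study participants, and treatment drop-outs are its example rather than its limit. This part of the reply stands: the loss arises only if a removed participant is in fact not assessed. What does not follow is that the promise settles the matter. It concerns staying in contact, and someone whose participation has been ended is not clearly still a study participant.

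The event may also be uncommon. Moderate or severe substance use disorder is an exclusion, the MINI substance module is given only at baseline, and the Severity of Dependence Scale is not given by telehealth. This limits the size but leaves the rule unchanged.

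A reader might further infer that the rule favours CABA, because CABA participants are seen far more often: ten sessions plus week 7, against week 7 alone in TAU. The documents do not support that conclusion. The wording about treatment visits belongs to the decline ground; the non-compliance ground names no point of detection. TAU participants are also contacted, since the site coordinator or study staff "will contact participants by phone to remind them of the initial visit, mid-treatment assessment, and post-treatment assessment", and medical records are a data source in both arms. CABA can itself address substance use, which could reduce removals there. An imbalance could run either way or be absent.

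**Conclusion.** The concern holds as a cheap improvement of minor weight. A stated, mandatory rule ends study participation where stopping treatment would do, and nothing clearly provides for assessment afterwards. Followed literally, it loses every post-baseline CAPS-V and hypothesis 1b value for those removed before week 14, for a reason probably related to outcome.

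The size and direction of any bias are unknown. Equal removals with equal outcome gaps only lose data. Under the assumed range (an imbalance of up to 4 participants either way, a gap of 0.5 to 1.0 SD, no baseline difference), the CAPS-V difference moves by at most about 0.04 SD in either direction, or 8% of the design effect. The reading of the text is firm; the figures only bound what those assumptions would produce.

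**What to change.** 1. In Section 5.7, change the consequence of non-compliance from ending participation to stopping study treatment with referral. In TAU, where there is no study treatment to stop, the consequence is referral only.
2. In the paragraph on voluntary withdrawal, extend the voluntary, paid week-7 and week-14 assessments to participants stopped by the investigators, unless the co-PIs judge the assessment itself unsafe.
3. Report, by arm, the number stopped and the number then assessed.

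No change to the analysis is needed. Once the data exist, the rule in Section 5.6 already keeps these participants in the analysis in their randomised arm. The co-PIs' discretion on safety is untouched.

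The text change is about two sentences. Each stopped participant adds at most one 60-minute and one 180-minute assessment (240 minutes, or four assessor hours) and 2 x $50 = $100. Both are already planned for every participant in Table 3 and in the reimbursement paragraph of Section 5.2.

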## **6.0 Reporting**

All SAE's, UAP's, and protocol deviations occurring at either site will be communicated to the Co-PI's immediately and necessary documentation will be submitted to the CIRB within stipulated timeframes and via designated channels in accordance with the VA Central IRB Table of Reporting Requirements.

## **7.0 Privacy and Confidentiality**

This study will involve the use and collection of Protected Health Information (PHI). Multiple steps will be taken in the current investigation to protect the privacy and confidentiality of research participants. All study personnel will have current training in GCP procedures for the proper use, collection, and disclosure of PHI for research purposes. Study personnel will no longer have access to study data upon termination of employment. Per VA protocol, in the event of improper use and/or disclosure, the local ISO and Privacy Officer will be notified within one hour. A code number will be assigned to each participant and his/her information. Only the multi-site co-PI's, the local site PI's, the multi-site project coordinator, and the site coordinator will be authorized to link the code number to the participant. A Master List will be retained by the study coordinator that will allow us to match each participant's code with their information; however, this Master List will be an electronic database that is password protected, and Informed Consent Forms will be stored in a double-locked cabinet apart from participant information. We will keep participant information in a separate electronic database that is password protected.

Participants who are assigned to the CABA condition will have their therapy sessions audio-recorded using a hand held digital audio recorder. However, these digital audio files will be identified by a number assigned to the participant and will not be marked with the participant's name or other identifying information. These audio-recordings will be listened to by a member of the research staff to determine if the interventions are conducted accurately ("adherence checks"). The audio files will be uploaded into a secure, password-protected folder on the VA network. These files will not contain identifying information audio recordings of sessions will be removed directly from the audio recorders immediately following the session to encrypted,

password protected, limited access drives on the VA network. Audio recorders with session content will not leave the session room before transfer.

**Adequacy of Privacy Protection.** We will take multiple steps to protect participants' privacy and confidentiality. All data will be labeled with a code number that is unique to each patient in the study, and maintained in a Subject Data File. We will NOT include any protected health information (PHI) in the Subject Data Files. Instead, we will code each Subject Data File with a unique numerical code, which will consist of the VA station number + 3 digits consecutively numbered in order of enrollment (e.g., 648-001, 648-002, etc.). All hard copy subject data will be stored in locked filing cabinets in locked rooms, while all electronic data will be stored in password-protected files in a limited access folder on the secure VA network drive. Each study site will maintain a Master List key code that links that site's subjects with their coded identifier. This key code will be stored separately from all other study data. Only the multi-site co-PI's, the local site PI's, the multi-site project coordinator, and the site coordinator will have access to the Master List key code, and only IRB-approved study personnel will have access to Subject Data Files or Informed Consent Forms. We will analyze and report subject data in aggregate form and no PHI will be entered into these analyses or reports.

